The concerns over metformin and renal impairment arise from the perceived risk of lactic acidosis in such patients. Lactic acid is produced when there is tissue hypoperfusion with resulting hypoxia. The condition occurs when the production of lactate exceeds its metabolism and removal. Risk factors for lactic acidosis include sepsis, shock, myocardial infarction, cardiac, respiratory or hepatic failure and hypoxemia.

Metformin associated lactic acidosis (MALA) has been reported, with a frequency ranging from 1 to 47 cases per 100,000 person years and a recent meta-analysis showed that the incidence of lactic acidosis wasn't higher among patients treated with metformin compared to those treated with other antidiabetics (57). On the other hand, as the mortality rate is around 50% this is a feared complication (58).

One study examined metformin levels in elderly patients with eGFR of 30-60 ml/min, or >60 ml/min, at doses of 850mg per day and 1700mg per day respectively. Metformin levels and plasma lactate levels were unchanged in both treatment groups, suggesting that metformin usage was safe in elderly patients with significant renal impairment (58).

A recent large cohort study conducted in the USA attempted to quantify the association between metformin use and hospitalization with acidosis across the range of eGFR, accounting for change in eGFR stage over time.

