3.2 Secondary objectives

Main secondary objective is to assess metformin efficacy (as compared to tolvaptan) in reducing the increase of TKV.

Moreover, it will be evaluated the rate of onset of metformin and tolvaptan related Adverse Events (AEs) namely Metfromin Associated Lactic Acidosis (MALA) and Acute Liver Injury (ALI), respectively.

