4.5 Unblind Treatment Period (Day 0 to Month 24)

Only subjects completing the IMP run-in period tolerating at least 45/15 mg of tolvaptan and 500/500 mg of metformin will be allowed upon entry to this unblind period.

In the metformin arm, during the treatment period visits will be scheduled every 3 months (each month has 28 days duration), within 3 days of the end of the trimester.

In tolvaptan treated patients, visits will be performed every month for the first 18 months, then every three months (each month has 28 days duration), within 3 days of the end of the month or the trimester (as prescribed by the additional monitoring requested by AIFA).

Beside the clinic visit and dispensing new bottles of IMP, subjects will have blood drawn on the last day of this period for efficacy and safety measures. The treatment duration of these subjects will be 24 months from the end of IMP run-in. Subjects not continuing in this trial will complete EoTx visit assessments and be followed for 7 days to assess any ongoing AEs.

From that point forward, every effort to maintain adherence and continuation of the subjects until the end of the trial should be undertaken. If continued tolerability becomes an issue, subjects may temporarily interrupt treatment as needed.

All subjects have the right to withdraw their consent from further participation in the trial at any time without prejudice.

Regardless of discontinuation of IMP, the subjects are expected to complete all monthly visits and assessments including the Month 24 visit.

4.6 Follow-up Period (up to Day +21 since Month 24 or End of Treatment)

Randomized subjects will enter the follow-up period after they complete the unblind, randomized treatment period, or after their EoTx visit, if they discontinued IMP. The follow-up period will be for 21 days in duration.

There will be no scheduled visits/assessments during the first week of the follow-up period. After the first week, 2 visits should be scheduled during the remaining 2 weeks of the follow-up period (between Day +8 and Day +21). The first visit should be scheduled on approximately Day +8, the second visit on approximately Day +21. These visits will be clinic visit.

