4.8 Measures to Minimize/Avoid Bias

Only subjects who reach Day -1 and are who have indicated that they would likely be able to tolerate the minimum dose of IMP "for the rest of their lives" at a level of 45/15 mg for tolvaptan and of 500/500 mg for metformin will be eligible to enter the un-blind, randomized treatment period.

Immediately prior to randomization, and at all subsequent visits or site-subject contacts, the subject will be reminded of the importance of their commitment to continue participation in the trial.

Randomization will be 1:1, tolvaptan:metformin. Randomization process will be carried out by a WEB-based, internet-accessible, system (e-trial platform). Investigators willing to include a patient should log-in into the e-trial platform and complete the registration form.

Each patient will be informed via a cover letter (that is the informed consent form) including clear instructions on participation, drug use, dosing and prescription.

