7. STUDY DURATION

7.1 Study Duration

The trial has a 36 months overall duration, that include a 9 months recruitment period.

7.1.1 Screening Period:

Has a 2 weeks duration, it is included in the 9 months recruitment period.

7.1.3 Treatment Period:

It has a 25 months duration. Each month lasts 28 days. It includes the 3 weeks titration period and the 1 week run-in period.

7.1.4 Post-Treatment Follow-up Period:

It lasts 21 days.

7.1.4 Total Study Duration:

About 3 years.

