8.2 Safety Endpoints

They include:

- changes from baseline in creatinine;
- vital signs;
- laboratory values including liver function tests, rate of aquaretic AEs, thus including serum sodium, rate of Metformin Associated Lactic Acidosis, blood insulin and glucose levels, HOMA test in both treatment groups.

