12. STATISTICAL CONSIDERATIONS

12.1 Sample Size Determination and Rationale

In TEMPO 3:4, tolvaptan reduced the decline in eGFR from 3.70 to 2.72 ml/min per 1.73 m² per year (26.5%); P=0.001). A post hoc analysis showed that tolvaptan decreased the rate of eGFR decline by 0.40 ml/min per 1.73 m² per year (95% CI, 20.25 to 1.05; P=0.23) in patients with CKD1, by 1.13 (95% CI, 0.61–1.66; P=0.001) in those with CKD2, and by 1.66 (95% CI, 0.83–2.45; P=0.001) in those with CKD3, with a trend for a positive subgroup–treatment interaction (P=0.07). Results for patients in CKD3 were similar when split into CKD3a and CKD3b. Tolvaptan treatment effects on eGFR slope were confirmed by comparing the eGFR values before treatment at baseline and those after discontinuation of study drug, which favored tolvaptan across CKD1 through CKD3. Consistent with the beneficial effects of tolvaptan on the rates of eGFR decline, patients with CKD2 and CKD3 randomly assigned to placebo were more likely to progress to a higher CKD stage at the last follow-up visit than those treated with tolvaptan.

This study will be based upon recruitment of an opportunistic sample given the rarity of the condition and the lack of available studies in the setting.

We plan to recruit a total of 150 patients which are currently within reach of the network coordinated by the proponent and composed by 11 Nephrology Centres. This network treats a total of 1500 (already genetically studied) patients of which we expect (based on standard response rates recognized in the population) acceptance to participate in the study to a value of approximately 40% of patients. These will be then allocated to the experimental and control intervention.

The selected sample is adequate to evaluate a significant reduction in the slope of eGFR at 2 years by 10%, which is a clinically relevant piece of information at the current state of knowledge, as well as a complete assessment of the benefits-harms trade-off of the two interventions.

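### At the rates the protocol cites, the sample cannot inform on metformin-associated lactic acidosis, so the claim of a complete benefit-harm assessment should be narrowed to common harms

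*Combined protocol and SAP*

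**What the plan says.** Section 12.1 calls the sample opportunistic and takes its size from what the network can reach: "We plan to recruit a total of 150 patients". It then declares that sample adequate to evaluate a 10% reduction in eGFR slope "as well as a complete assessment of the benefits-harms trade-off of the two interventions". The statistical part of the synopsis says the same. Neither place gives an expected event count, a precision target or power for any harm.

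Section 3.2 names kidney volume as the main secondary objective. It adds evaluation of the rates of onset of MALA and acute liver injury (ALI), attributed to metformin and tolvaptan respectively. Section 8.2 lists "rate of Metformin Associated Lactic Acidosis" next to vital signs, liver tests, sodium and aquaretic events, glucose, insulin and HOMA.

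Section 2.2.2 says MALA has been reported "with a frequency ranging from 1 to 47 cases per 100,000 person years", puts its mortality at around 50%, and concludes that lactic acidosis seems rare in CKD patients on metformin. Section 12.3 plans frequencies and percentages for categorical variables and a 0.05 threshold. It gives no rule for rare harms.

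**The concern.** MALA is the harm the protocol singles out for metformin, and by its own account the most dangerous one. An assessment that cannot inform on it is not complete. With so little exposure, zero cases is the likely result if metformin is as safe as cited, and about an even chance if the true rate is ten times the top cited figure. Because the plan sets no upper-limit rule, nothing in it guards against a bare count of zero being read as having answered the MALA objective. That would matter in a trial proposing a cheap alternative to the approved drug.

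**Working it through.** **The plan's own figure.** There is none to reproduce. No event count, precision or power for harms is stated, so the check sets the protocol's incidence against its exposure.

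**Inputs**
- Sample: 150 (section 12.1).
- Allocation: "Randomization will be 1:1, tolvaptan:metformin" (section 4.8), so about 75 on metformin.
- Exposure after run-in: "The treatment duration of these subjects will be 24 months from the end of IMP run-in" (section 4.5).
- Full treatment period and month length: "It has a 25 months duration. Each month lasts 28 days" (section 7.1); this includes titration and run-in.
- Reported MALA incidence: 1 to 47 per 100,000 person-years (section 2.2.2).
- Assumptions: that range applies to these patients, and all 75 complete. Dropout, titration failure and run-in failure would lower the exposure.

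**Person-years (PY)**
- After run-in: 75 × 24 × 28 / 365.25 = 138.0.
- With titration and run-in: 75 × 25 × 28 / 365.25 = 143.7.

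**Expected cases = PY × rate**
- Lowest: 138.0 × 1/100,000 = 0.0014.
- Highest: 143.7 × 47/100,000 = 0.068.

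**Chance of at least one case = 1 − exp(−expected)**
- Lowest: 0.14%.
- Highest: 1 − exp(−0.0676) = 6.5%.
- With 24 calendar months instead (150 PY), the top expected count is 0.0705 and the chance 6.8%.

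**Upper 95% limit if no case occurs**, −ln(0.05)/PY one-sided and −ln(0.025)/PY two-sided, per 100,000 PY

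| PY | One-sided | Two-sided |
|---|---|---|
| 143.7 | 2.996/143.7 = 2,084 | 3.689/143.7 = 2,567 |
| 138.0 | 2.996/138.0 = 2,171 | 3.689/138.0 = 2,673 |

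Against the top cited rate, 2,084/47 = 44 and 2,673/47 = 57. As a cumulative risk with 0 of 75, the limit is 1 − 0.05^(1/75) = 3.9% one-sided and 1 − 0.025^(1/75) = 4.8% two-sided.

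**How far off the design is**
- One expected case at the top rate needs 100,000/47 = 2,128 PY, about 15 times 143.7.
- At ten times the top rate (470 per 100,000), 138.0 PY gives 0.65 expected cases, and exp(−0.65) = 52% chance of none.
- An 80% chance of one case needs a true rate of −ln(0.2)/138.0 = 1,166 per 100,000, about 25 times the top rate.
- With 75 per arm, Fisher's exact test (two-sided) gives p = 0.058 for 5 versus 0 and p = 0.028 for 6 versus 0, so at least six cases would be needed.

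**Sensitivity to a broader event.** The cohort described in section 2.2.2 had 2,335 hospitalisations with acidosis among 75,413 patients, with median follow-up of 5.7 years. Taking the median as the mean, 2,335/(75,413 × 5.7) = 543 per 100,000 PY. On 143.7 PY that is 0.78 expected events and exp(−0.78) = 46% chance of none. Even this wider event is expected less than once.

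**The case against.** Several points on the other side have force.

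- **The plan contains no wrong sum.** It makes a qualitative claim and discloses both the rarity of lactic acidosis and the opportunistic sample. This stands: the fault is an overstated property of the design, not a miscalculation.
- **A reader might infer that the harms assessment as a whole fails.** The documents do not support that. Section 8.2 lists commoner harms that about 75 patients per arm can compare, and no ALI rate is given, so the ALI half of the objective cannot be judged either way.
- **A reader might infer that a formal between-arm test of MALA is planned.** Section 3.2 speaks only of evaluating rates of onset and assigns MALA to metformin. A count is already within section 12.3; the upper limit and the caveat are what is missing.
- **A reader might infer that zero cases would be no evidence at all, or that the plan treats zero as proof of safety.** Neither holds. Zero of 75 would exclude a cumulative risk above about 4–5%, and no section says that zero establishes safety.
- **The incidence is borrowed.** Section 2.2.2 gives reported MALA, not specific to non-diabetic ADPKD. Excluding hypoxic disease, requiring eGFR of at least 45 and listing a fall below 30 as a metformin discontinuation reason point to a lower rate; systematic blood gases could raise ascertainment. Sections 10.1.3, 10.6 and 11 also use different lactate and pH criteria. So the true rate under the trial's count is unknown, though it would have to be many times the cited top to change the conclusion.
- **A lactate comparison has no stated precision either.** True. The documents give no spread for lactate, so none can be computed for the means. For a proportion, the worst-case 95% half-width is 1.96 × √(2 × 0.25/75) = 16 percentage points. Blood gas is measured locally at about 11 sites, so differences between sites must be allowed for.

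**Conclusion.** The concern holds for MALA. Assuming the cited range applies and all 75 patients complete, the trial expects 0.0014 to 0.068 cases, has at most about a 6.5% chance of seeing one, and with none could exclude only rates above about 2,100 to 2,700 per 100,000 person-years. The MALA part of the section 3.2 objective therefore cannot be informatively estimated or compared, and the word complete in section 12.1 and the synopsis is not supported.

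The conclusion goes no further than that. It does not touch common harms, says nothing about ALI, and leaves the primary analysis unaffected. The 10% slope claim in the same sentence is a separate matter.

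**What to change.** - **Synopsis and section 12.1:** replace the claim of a complete assessment with a statement that the sample supports comparison of common harms only.
- **Sections 3.2 and 8.2:** keep MALA as a descriptive count under one stated definition, after reconciling the criteria in sections 10.1.3, 10.6 and 11. Report it with its exact upper confidence limit, and state that zero cases does not establish safety at the cited rates.
- **Sections 8.2 and 12.3:** add a between-arm comparison of venous lactate and pH, and of the proportion with lactate above 2 mmol/l (a threshold already in section 10.6). Use the three-monthly visits common to both arms, because tolvaptan patients are also seen monthly for the first 18 months. Allow for site, and present estimates with confidence intervals.

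Blood gas is already scheduled at these visits in both arms (sections 9.1.4 and 10.3, and Figure 1), so no extra patients or procedures are needed. The cost is wording, one extra table and a less favourable stated claim.

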12.2 Randomization

Randomization process will be carried out by a WEB-based, internet-accessible, system (e-trial platform). Investigators willing to include a patient should log-in into the e-trial platform and complete the registration form.

12.3 Statistical Methods

A comparative analysis for the primary outcome will be carried out under the principle of "intention-to-treat" and including data from all subjects who are randomized. The efficacy and safety of compared interventions will be assessed. Trial data will be summarized by the calculation of means and standard deviations for normally distributed variables, medians and interquartile ranges for non-normally distributed variables, and frequency and percentage for categorical variables. Missing data will be ignored. The primary and secondary outcomes, namely the slope of the annualized eGFR and TKV will be analyzed using standard statistics including linear mixed-effects models. A P value <0.05 will be deemed significant.There are no plans for interim analyses.

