Randomization visit will occur on Day -29. During this visit patients will be randomized (in a ratio 1:1 tolvaptan:metformin) to each arm of treatment and will start an **IMP titration period** (3 weeks from -28 to -8). Subjects not tolerating the minimum IMP dose will be considered "Titration failures" and will complete End of Treatment (EoTx) visit assessments and will be followed up after 7 days by phone call to assess any ongoing AEs. Subjects tolerating the minimum IMP dose enter the unblind **run-in period** (1 week from Day -7 to -1). During the "Run-in" phase, subjects will continue on a stable IMP dose to confirm tolerability over a longer period. At the end of the run-in period (Day -1), subjects not tolerating the minimum IMP dose will be considered "Run-in failures" and will complete EoTx visit assessments and will be followed up after 7 days by phone call to assess any ongoing AEs. Subjects completing the run-in will start the open-label **24 months treatment period**, during which visits will be collected three-monthly. At the end of the 24th month, and in case of early treatment cessation, **follow-up period** (3 weeks from +8 to +21) will start, during which 2 visits have to be collected. No IMP will be administered during this period.

Assessments at the Randomization (Day -29), End of IMP Run-in Period (Day -1), End of each three-monthly of on-therapy period will include those for points 2 to 8 of screening period plus IMP dispensation.

Assessments during EoTx Visits (in case of Titration failure, Run-in failure, early treatment cessation) and Follow-up visits will include those for points 2 to 8 of screening period. Non contrast enhanced CT-scan of the kidneys for TKV measurement will be also performed at the end of Month 24.

Patients treated with tolvaptan, will anyhow undergo monthly visits during the first 18 months of therapy (as prescribed by the additional monitoring requested by AIFA), then every three months.

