4.2 Randomization visit (Day -30)

Randomization process will be carried out by a WEB-based, internet-accessible, system (e-trial platform). Investigators willing to include a patient should log-in into the e-trial platform and complete the registration form.

The patient allocation number and the treatment arm will be immediately TRASMITTED on line without blinding.

Any controversial eligibility assessment will be discussed with the Study Chair.

Each patient will be informed via a cover letter including clear instructions on participation, drug use, dosing and prescription.

Randomization visit may coincide with CT-scan visit.

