4.3 IMP Titration Period (since Day -28 up to Day -8)

Subjects randomized in tolvaptan arm will be given a split dose of 45/15 mg tolvaptan (unblind) with upward titration every 7 days to 45/15 mg, 60/30 mg, up to a maximum dose

of 90/30 mg per day over 3 weeks. Jinarc® has to be taken between meals; the first dose upon waking and the second dose after eight hours from the first.

Dose up-titration will be done after tolerability check (by phone call the patient will be asked: "Are you having troubles taking this drug? Are you able to tolerate this dose for the rest of your life?"). Up-titration will be done the day after tolerability check, in Day -22 and in Day -15.

Subjects who are unable to tolerate at least 45/15 mg of daily tolvaptan will be considered "Run-in failures" and will complete an EoTx visit and be followed up after 7 days by phone call to assess any ongoing AEs.

Subjects randomized to metformin arm will be given a single dose of 500 mg of metformin for the first week (unblind), then a split dose of 500/500 mg metformin with upward titration after 7 days to 500/500/500 mg, (that is the maximum trial dose of metformin per day). Zuglimet® has to be taken between meals; the first dose upon waking, the second and the third daily dose after eight hours from the previous dose.

Dose up-titration will be done after tolerability check (by phone call the patient will be asked: "Are you having troubles taking this drug? Are you able to tolerate this dose for the rest of your life?"). Up-titration will be done the day after tolerability check, in Day -22 and in Day -15.

Subjects who are unable to tolerate at least 500/500 mg of daily metformim will be considered "Run-in failures" and will complete an EoTx visit and be followed up after 7 days by phone call to assess any ongoing AEs. Subjects tolerating the minimum IMP dose will enter the unblind run-in period (1 week from Day -7 to -1).

Assessments during up-titration phone call will include:

1) Assess IMP tolerability

2) Assess AEs, if reported

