4.4 IMP Run-in Period (since Day -7 up to Day -1)

Subjects tolerating at least 45/15 mg tolvaptan or 500/500 mg metformin may enter the unblind, run-in period (1 week duration). Subjects will continue on a stable IMP dose to confirm tolerability over a longer period.

At the end of the run-in period, subjects not tolerating at least 45/15 mg tolvaptan or 500/500 mg metfromin will be considered "Run-in failures". They will complete EoTx visit assessments and be followed up after 7 days by phone call to assess any ongoing AEs.

Subjects found ineligible to be randomized and continue in this trial must have a 7-day follow-up visit.

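### Titration and run-in failures are randomised patients under contradictory follow-up rules; if the 7-day exit is applied, the all-randomised slope comparison becomes in effect one of run-in completers

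*Combined protocol and SAP*

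**What the plan says.** **Analysis.** Section 12.3 defines the primary comparison as intention-to-treat, "including data from all subjects who are randomized", using linear mixed-effects models. On incomplete follow-up it says only "Missing data will be ignored".

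**Order of events.** Randomisation is on Day -29 (section 4) or Day -30 (section 4.2). Allocation is open: "The patient allocation number and the treatment arm will be immediately TRASMITTED on line without blinding". Titration (Day -28 to -8) and run-in (Day -7 to -1) follow on the allocated drug.

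**Failures.** Section 4 says that titration and run-in failures "will complete EoTx visit assessments and will be followed up after 7 days by phone call to assess any ongoing AEs". Section 4.3 says "Subjects who are unable to tolerate at least 500/500 mg of daily metformim will be considered" run-in failures, with a parallel rule for tolvaptan at 45/15 mg. Section 11 places the end-of-treatment visit at the point where the patient leaves the trial, gives run-in failures a 7-day call unless they have fully withdrawn consent, and lists nothing after it.

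**Anyone who stops after randomisation.** Section 11.2 takes such patients through the 21-day follow-up period and then all assessments to Month 24. Section 4.6 sends randomised subjects into that follow-up period at the end of treatment "or after their EoTx visit, if they discontinued IMP". Section 5.4 requires continued follow-up unless withdrawal is documented. Section 10.2 collects creatinine to the scheduled end of trial, but only for patients who remain in the trial.

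**The concern.** The same patients fall under two incompatible rules. Several sections are also worded as if randomisation came after run-in. Section 4.4, describing the end of run-in, says "Subjects found ineligible to be randomized and continue in this trial must have a 7-day follow-up visit". Section 10.2 reserves 7 days of adverse-event follow-up for patients who stopped before randomisation and gives randomised patients 21 days. Sections 10.5.1.1 and 10.5.1.2 bar or defer randomisation on liver tests taken during tolvaptan titration or run-in. Section 11 labels titration and run-in as periods before randomisation.

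A site that follows the failure-specific text would release randomised patients with almost no outcome data. The filters differ by arm: the minimum dose is the first titration step for tolvaptan and the second for metformin, and the liver-test disqualification names only tolvaptan. Patients know their arm when they judge tolerability. At stake are the primary slope comparison and the Month 24 htTKV comparison. Sites could differ in the rule they apply, and the data collected could not show the size or direction of any bias.

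**Working it through.** **1. Are failures randomised?** Months are 28 days. Section 4.7 puts the last scheduled treatment 25 months after randomisation: 25 × 28 = 700 days. From Day -29 to Month 24 is 672 + 29 = 701 days; from Day -30, 702; from Day 0, 672. The 25 months fit randomisation before titration, so failures are randomised patients.

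**2. How many?** 150 patients at 1:1 is 75 per arm (sections 12.1 and 4.8). Failure rates are not given. Assume 10-20% on tolvaptan and 5% on metformin:
- 75 × 0.10 + 75 × 0.05 = 11.25 failures, leaving 67.5 and 71.25 completers.
- 75 × 0.20 + 75 × 0.05 = 18.75 failures, leaving 60 and 71.25.

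**3. How much slope information does a failure carry?** The measure is the sum of squared deviations of the creatinine times, in years². Screening samples are assumed at Days -40 and -38.
- Completer: two screening values, Day -1 and eight visits 84 days apart give 4.90, or 5.51 with a Day -29 value. The two post-treatment values are left out; including them raises this to about 7.1-8.0 and shrinks the ratios below.
- Failure under the 7-day exit: screening values, with or without Day -29, and one end-of-treatment value between Day -21 and Day 0. The ratio to a completer runs from 0.0017/5.51 = 0.03% to 0.0076/4.90 = 0.16%.
- Allowing a failure up to two follow-up values as well, the upper limit is 0.0230/4.90 = 0.47%. With screening extended by 8 weeks it stays below 2%.

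**4. Does the mixed model recover the lost patients?** I used a random intercept and slope model with linear trends, failure fraction 5-20%, residual SD 3-8, slope SD 2-5 and intercept SD 15, all assumed. With no follow-up values, at least 97% of any bias remains. With up to two follow-up values, at least 91% remains, or at least 72% if every screening were extended by 8 weeks. Failures are nominally in the model but barely affect the slope.

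**5. Bias.** Let p be an arm's failure fraction and d the mean slope of its failures minus that of its completers. The completer contrast (metformin minus tolvaptan) differs from the all-randomised contrast by p_T·d_T − p_M·d_M. With a common gap d this is (p_T − p_M)·d:
- 10% v 5%, d = 2: 0.05 × 2 = 0.10.
- 20% v 5%, d = 2: 0.15 × 2 = 0.30.
- Equal failure rates with a common gap, or tolerance unrelated to slope: 0.
- Opposite gaps of +2 and -2 at 20% and 5%: 0.40 + 0.10 = 0.50, so 0.30 is not an upper bound.

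**6. Against the plan's target.** Section 12.1 gives no SD or power, so the sample of 150 cannot be reproduced. Its 10% effect is 0.272 on the quoted slope of 2.72, or 0.37 on 3.70. A bias of 0.272 needs a gap of 0.272/0.15 = 1.81 (20% v 5%) or 0.272/0.05 = 5.44 (10% v 5%).

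**7. Error rate.** SE = SD × √(1/n_T + 1/n_M), with slope SD assumed 2-4. The two-sided error is Φ(−1.96 + b/SE) + Φ(−1.96 − b/SE).

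| Completers | Bias b | SD | SE | b/SE | Error |
|---|---|---|---|---|---|
| 60 and 71.25 | 0.30 | 2 | 0.350 | 0.86 | 13.7% |
| 60 and 71.25 | 0.30 | 4 | 0.701 | 0.43 | 7.1% |
| 67.5 and 71.25 | 0.10 | 2 | 0.340 | 0.29 | 6.0% |
| 67.5 and 71.25 | 0.10 | 4 | 0.679 | 0.15 | 5.2% |

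**8. Which early creatinines exist?** Section 4 assigns screening point 8 (blood samples) to Day -29 and to the end-of-treatment visit of failures. Section 9.1.2 lists no bloods at randomisation, section 11 ties the end-of-treatment bloods to a second visit, and Figure 1 has a column for neither visit.

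**The case against.** The best defence is that the 7-day contact concerns adverse events only, and no sentence says creatinine collection stops. Section 5.4 separates stopping drug from withdrawing consent. Section 4.5 expects visits through Month 24 despite discontinuation, and sections 4.6, 10.2 and 11.2 point the same way. On that reading the intention-to-treat set is safe. The two figures whose content is not available might also show the path of failures.

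This reading is possible but not secure. Section 10.2's creatinine rule excludes patients who have left the trial, which is how section 11 describes failures. The 4.5 sentence sits in the treatment-period section, which only run-in completers enter. That section also counts its 24 months from the end of run-in, a date that a titration failure never reaches.

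The objection to the size largely stands. Every input is assumed, nothing in the documents links tolerability to slope, and the 14% error needs the unfavourable assumptions together. Tolvaptan need not be the arm with more failures, because metformin's minimum dose is its second step. This limits what can be said about magnitude, but it does not remove the contradiction.

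**Conclusion.** The concern holds and must be fixed. The protocol gives two incompatible follow-up rules for randomised patients who fail titration or run-in, and section 12.3 does not say how they enter the analysis. If sites follow section 11.2, the comparison is protected. If they follow the failure-specific text, the all-randomised analysis is one in name only.

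Under the assumptions above the bias ranges from zero to about the size of the plan's own target, in either direction. The severity does not rest on the worst case. It rests on a primary population that is not operationally defined and on two-year outcomes that cannot be collected afterwards. Confidence is high in the contradiction and in the negligible information from released failures; the size of any bias is unknown.

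**What to change.** 1. State in sections 4, 11 and 12.3 that every randomised patient, including titration and run-in failures, stays under section 11.2 unless consent is withdrawn. This covers the scheduled creatinines (at least the quarterly visits common to both arms) and the Month 24 CT, with the existing pregnancy exception in 10.1.11 unchanged. Define Month 24 for failures, for example from the randomisation date as in 4.7. Keep these patients in the primary set whatever treatment they later take, and make the run-in-completer analysis supportive only.
2. Reconcile the wording in 4.4, 10.2, 10.5.1.1 (including its rescreening provision), 10.5.1.2 and 11 with the actual time of randomisation. Reconcile sections 4, 9.1.2, 11 and Figure 1 on which early visits include creatinine. No dose, safety or stopping rule needs to change for this.
3. Report titration and run-in failures, with reasons, by arm. Use one definition of each: section 4 calls failures during titration titration failures, and section 4.3 calls them run-in failures.
4. Replace the missing-data sentence. Report by arm the randomised patients with no creatinine after Day 0, and add a sensitivity analysis that shifts their mean slope over a stated range, for example -2 to +2 ml/min/1.73 m² per year, separately by arm.

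**Cost.** Amendment wording, one sensitivity analysis and visit types already in the schedule. Under the assumed failure rates this is 11.25 × 8 = 90 to 18.75 × 8 = 150 quarterly visits and 11-19 CTs, plus the two follow-up visits of 11.2 (11.25 × 2 = 22.5 to 18.75 × 2 = 37.5). If the monthly tolvaptan schedule of 4.5 were also applied to tolvaptan-arm failures (20 visits each), the scheduled visits would be 7.5 × 20 + 3.75 × 8 = 180 to 15 × 20 + 3.75 × 8 = 330; the fix asks only for the quarterly ones. The statistical price is some dilution of a true difference, because patients off the allocated drug stay in the primary analysis.
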